5.4.1 NITROGLYCERIN PHARMACOLOGY

Nitroglycerin is a vasodilator and antianginal agent, that can be administer intravenously, orally, intra-anal, as a topical agent, as a patch, sublingual and as a translingual spray. In our study it will be administered via intravenous infusion as previously specified by the protocol.

5.4.1.1 NITROGLYCERIN HUMAN TOXICITY

Nitroglycerin serious adverse reactions include severe hypotension, nitrates tolerance, bradycardia, anaphylactoid reactions, and methemoglobinemia. Other common reactions include headaches, lightheadedness, dizziness, flushing, orthostatic hypotension, reflex tachycardia, edema, burning oral sensation (sublingual use) and tingling oral sensation (sublingual use).

5.4.1.2 SEVERE HYPOTENSION

The most common adverse effect of Nitroglycerin is hypotension. Nitroglycerin forms free radical nitric oxide. In smooth muscle, nitric oxide activates guanylate cyclase which increases guanosine 3'5' monophosphate (cGMP) leading to dephosphorylation of myosin light chains and smooth muscle relaxation. This produces a vasodilator effect on the peripheral veins and arteries with more prominent effects on the veins, decrease preload (left ventricular end-diastolic pressure); may modestly reduce afterload. This can lead to severe hypotension and paradoxical bradycardia and increased angina pectoris can accompany hypotension.

5.4.1.3 METHEMOGLOBINEMIA

Methemoglobinemia is an uncommon side effect of nitroglycerin use. Methemoglobin is an oxidized form of hemoglobin that has a decreased affinity for oxygen, resulting in an increased affinity of oxygen to other heme sites and overall reduced ability to release oxygen to tissues. The oxygen-hemoglobin dissociation curve is therefore shifted to the left when it's present. When methemoglobin concentration is elevated in red blood cells, tissue hypoxia can occur. The protective enzyme systems normally present in red blood cells maintain methemoglobin levels at less than one percent of the total hemoglobin in healthy people. Exposure to exogenous oxidizing drugs and their metabolites such as nitrates may accelerate the rate of formation of methemoglobin up to one-thousand fold, overwhelming the protective enzyme systems and acutely increasing methemoglobin levels.

5.4.1.4 NITROGLYCERIN DRUG TO DRUG INTERACTIONS

Nitroglycerin is relatively safe medication. Some medications can cause severe or fatal adverse reactions. Interaction risk stratification is done following the following classification:

- A - No known interaction
- B - No action needed
- C - Monitor therapy
- D - Consider therapy modification
- X - Avoid combination

- Alfuzosin: May enhance the hypotensive effect of Nitroglycerin. *Risk C: Monitor therapy*
- Alteplase: Nitroglycerin may decrease the serum concentration of Alteplase. *Risk C: Monitor therapy*

- Ergot Derivatives: May diminish the vasodilatory effect of Nitroglycerin. This is of particular concern in patients being treated for angina. Nitroglycerin may increase the serum concentration of Ergot Derivatives. *Risk X: Avoid combination*
- Heparin: Nitroglycerin may diminish the anticoagulant effect of Heparin. Nitroglycerin may decrease the serum concentration of Heparin. *Risk C: Monitor therapy*
- Hypotensive Agents: May enhance the adverse/toxic effect of other Hypotensive Agents. *Risk C: Monitor therapy*
- Phosphodiesterase 5 Inhibitors: May enhance the vasodilatory effect of Vasodilators (Organic Nitrates). *Risk X: Avoid combination*
- Prilocaine: Methemoglobinemia Associated Agents may enhance the adverse/toxic effect of Prilocaine. Combinations of these agents may increase the likelihood of significant methemoglobinemia. Management: Monitor patients for signs of methemoglobinemia (e.g., hypoxia, cyanosis) when prilocaine is used in combination with other agents associated with development of methemoglobinemia. Avoid lidocaine/prilocaine in infants receiving such agents. *Risk C: Monitor therapy*
- Rosiglitazone: Vasodilators (Organic Nitrates) may enhance the adverse/toxic effect of Rosiglitazone. Specifically, a greater risk of myocardial ischemia was reported for users of this combination in a meta-analysis. Management: Consider alternatives to this combination when possible. Rosiglitazone prescribing information states that the combination of rosiglitazone and a nitrate is not recommended. *Risk D: Consider therapy modification*
- Ethanol: Avoid ethanol (may increase the hypotensive effects of nitroglycerin). Monitor.
- Herb/Nutraceutical: Avoid bayberry, blue cohosh, cayenne, ephedra, ginger, ginseng (American), kola; licorice (may worsen hypertension). Avoid black cohosh, California poppy, coleus, golden seal, hawthorn, mistletoe, periwinkle, quinine, shepherd's purse (may cause hypotension).

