4.3 SAMPLE AND METHODOLOGY

We will enroll 400 patients with a Mehran score of 6 or more that have a pre-procedural creatinine measured. Following baseline assessments, patients will be randomly assigned to receive intravenous infusion nitroglycerine plus intravenous normal saline or normal saline only.

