5.2.2 INCLUSION CRITERIA

All of the following inclusion criteria must be present for the patient to be enrolled in the trial.

- 1- Patient must be scheduled for percutaneous angiography, defined as diagnostic cardiac catheterization, or lower extremity or aortic iodinated contrast angiography.
- 2- Patients must have a Mehran score of at least 6 before the procedure.
- 3- Patients must have baseline creatinine and hemoglobin drawn before the procedure.
- 4- Signed informed consent.

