5.2.3 EXCLUSION CRITERIA

None of the following exclusion criteria must be present for the patient to be enrolled in the trial

- 1- Patients on renal replacement therapy before randomization, will be excluded.
- 2- Being exposed to any types of nitrates 48 hours prior to randomization,
- 3- History of allergic reaction to any of the components of intravenous nitroglycerin.
- 4- Exposure to contrast media 4 days prior randomization.
- 5- Planned revascularization in the next 24 to 48 hours of the first PCI procedure.
- 6- The patient is hypotensive (<90/60mmHg) at the time of randomization.
- 7- Patients exposed to phosphodiesterase inhibitors 48 hours prior to randomization

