5.2.4 SCREENING AND BASELINE EVALUATION

Potentially eligible patients will undergo an initial evaluation in which eligibility will be confirmed and the trial protocol explained in detail. All willing and eligible patients providing informed consent will have baseline data obtained including relevant history and use of all conventional and alternative therapies. Baseline laboratory tests will be performed and information on quality of life will be obtained.

The following variables will be obtained for all patients included in the trial: age, gender, weight, height, body mass index, blood pressure, left ventricular ejection fraction, hypertension, diabetes mellitus, peripheral vascular disease, medication use (angiotensin converting enzyme inhibitors, calcium channel blockers, beta blockers, statins, ascorbic acid, acetylcysteine, angiotensin receptor blockers, diuretics, aspirin), PCI (number of vessels) smoking status, amount of contrast, type of contrast, amount of hydration, serum hemoglobin, serum sodium, serum potassium, baseline creatinine and post procedure creatinine, glomerular filtration rate.

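### Two drug groups carry the protocol's top interaction rating with nitroglycerin, but only one is carried over into the exclusion criteria, so an ergot user can be randomised

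*Combined protocol and SAP*

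**What the plan says.** Section 5.4.1.4 grades drug interactions with nitroglycerin on a five-level scale from A to X, where X means that the two drugs should not be given together. Two groups receive an X.

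- Ergot derivatives. The entry says that ergots may weaken nitroglycerin's vasodilatory effect, adds "This is of particular concern in patients being treated for angina", and ends "Nitroglycerin may increase the serum concentration of Ergot Derivatives. *Risk X: Avoid combination".
- Phosphodiesterase-5 inhibitors: "Phosphodiesterase 5 Inhibitors: May enhance the vasodilatory effect of Vasodilators (Organic Nitrates). *Risk X: Avoid combination".

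Section 5.2.3 has seven exclusion criteria. Two concern recent exposure to a drug class with vascular effects: item 2, "Being exposed to any types of nitrates 48 hours prior to randomization", and item 7, "Patients exposed to phosphodiesterase inhibitors 48 hours prior to randomization". The other five are renal replacement therapy, allergy to a component of the infusion, recent contrast, planned revascularisation and hypotension. The four inclusion criteria in section 5.2.2 concern the procedure, the risk score, baseline laboratory values and consent.

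At baseline, section 5.2.4 collects "relevant history and use of all conventional and alternative therapies". Section 4.3 places this before allocation: "Following baseline assessments, patients will be randomly assigned to receive intravenous infusion nitroglycerine".

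**The concern.** The protocol turns one of its two Risk X ratings into an enrolment rule and leaves the other as a warning. It gives no reason for the difference. Eligibility is verified against the written criteria before the randomisation screen is completed (section 5.2.5), so a drug missing from those criteria is not something the check is designed to find.

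What is at stake is exposure of an individual patient to a combination that the protocol says to avoid. By its own account, nitroglycerin may raise the ergot level and the ergot may blunt nitroglycerin's effect. This matters for patient safety and for consistency within the protocol; it does not bear on the trial's inference.

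**Working it through.** The check is mainly a comparison of texts, with a little counting.

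**1. Ratings in section 5.4.1.4.** Eight drug groups carry a letter.

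| Rating | Groups | Count |
|---|---|---|
| C | alfuzosin, alteplase, heparin, hypotensive agents, prilocaine | 5 |
| D | rosiglitazone | 1 |
| X | ergot derivatives, phosphodiesterase-5 inhibitors | 2 |

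5 + 1 + 2 = 8. Ethanol and the herbal products are listed without a letter.

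**2. Risk X groups against the eligibility lists.**

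| Risk X group | Inclusion (5.2.2) | Exclusion (5.2.3) |
|---|---|---|
| Phosphodiesterase-5 inhibitors | none | item 7, 48 hours |
| Ergot derivatives | none | none |

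One of the two is covered. In the available text, ergots appear only in section 5.4.1.4. Item 2 removes recent nitrate users, but nitrates are the study drug's own class, not a Risk X entry.

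**3. Other points where an ergot user might be stopped.**

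- *Baseline history (5.2.4).* It covers all therapies, so ergot use could come to light. No rule says what follows, and ergots are not among the medications named there.
- *Ordering the treatment (5.2.5).* The coordinator enters the order in the chart and starts an infusion stocked in advance. The warning could be applied at this step, but no interaction check is assigned to it.
- *Pharmacist (3.2 and 5.2.5).* The pharmacist shares responsibility for handling the product and has access to the randomisation list, but is given no task of screening for interactions.
- *Second screen (5.3, step 7).* It repeats the exclusion criteria, so it inherits the same omission, and it comes after the first infusion (step 6).
- *Safety outcome (4.2).* Medication interaction is recorded, but only after exposure.

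**4. Exposure of one enrolled ergot user.** Section 5.1 sets 1:1 allocation, so the chance of nitroglycerin is 1/(1 + 1) = 0.5. Section 5.4 plans at least 1 hour before and 3 hours after the procedure, so the minimum is 1 + 3 = 4 hours. These figures describe any randomised patient; they show what an ergot user would be exposed to, not how many there are.

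**5. Sample size.** The plan gives no figure on the ergot question. Its only power figure, 161 per arm in section 5.1, reproduces from a control rate of 0.30, an experimental rate of 0.30 × 0.5 = 0.15, power 0.9 and two-sided alpha 0.05, without continuity correction:

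n = [1.960 × √(2 × 0.225 × 0.775) + 1.282 × √(0.30 × 0.70 + 0.15 × 0.85)]² / 0.15² ≈ 160.8, rounded up to 161.

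Ergot use is not an input, so the figure stands with or without the fix.

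**The case against.** Four arguments deserve weight.

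*The protocol already says to avoid the combination.* Section 5.4.1.4 sits under the treatment regimens, so staff who follow it would not give nitroglycerin to an ergot user. On that reading the defect is a missing cross-reference. This is largely fair, and it is why the right description is that the rating does not carry over. A reader might infer that the eligibility list contradicts the rating. It does not: it is silent, and no criterion positively admits ergot users. But the phosphodiesterase-5 warning is in the same list, and the authors still wrote item 7 for it.

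*The interaction list may be general drug information.* It advises on infants and tells the reader to avoid ethanol and several herbs, none of which has an exclusion. That is true, but those items carry no letter rating. The comparison here is between two groups with the same rating.

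*The two groups differ pharmacologically.* Phosphodiesterase-5 inhibitors add to vasodilation, and section 5.4.1.2 names hypotension as the most common adverse effect; ergots oppose vasodilation. This may explain the priority given to item 7. The protocol does not say so, and it also names a rise in ergot concentration.

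*The angina sentence.* The trial recruits cardiac patients ("Patient must be scheduled for percutaneous angiography, defined as diagnostic cardiac catheterization"), so a reader might infer that "This is of particular concern in patients being treated for angina" marks them as being at special hazard. The documents do not support that. The sentence follows directly on the statement that ergots weaken nitroglycerin's effect, so its natural meaning is loss of antianginal benefit. Here nitroglycerin is given to protect the kidney. The point rests on the Risk X rating and the two stated interactions, without the angina argument.

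**Conclusion.** The point holds as a minor patient-safety inconsistency. Of two groups with the protocol's top interaction rating, one has an exclusion and one has none. As written, an ergot user can satisfy all four inclusion criteria, trigger none of the seven exclusions, and be randomised to nitroglycerin. The safeguards reduce the chance of this, but none is tied to eligibility.

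The size in patients is unknown. The documents give no frequency of ergot use; that it is low in this population is my assumption. The documents also name no clinical consequence of a raised ergot level, so no rate of harm can be derived. A reader might infer that blunted vasodilation in ergot users would dilute the treatment effect and cost power; without a frequency or an effect size, nothing in the documents supports such a claim, and none is made.

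The conclusion is limited to the text available for review.

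**What to change.** Add to section 5.2.3 an exclusion for current or recent use of ergot derivatives. It should state one fixed washout, set by the investigators and the pharmacist from the pharmacology of the ergot products concerned. The 48 hours in item 7 should not simply be copied: it belongs to a different drug class, and the documents give no ergot pharmacology to support it. An open-ended period left to judgement would not be a usable criterion either.

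Add one sentence to section 5.4 barring ergot use during the infusions before and after the procedure. Because the check is then made before allocation, it applies equally to both arms, and the second screen in section 5.3 picks it up without further change.

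The cost is two lines of text and the loss of the few eligible patients who take ergots, each of whom needs one replacement to reach the planned 400.

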6.0 THE USE OF NITRATES FOR THE PREVENTION OF CIN

See retrospective study attached - Exhibit A

7.0 BUDGET

See Budget proposal attached- Exhibit B

